5. STUDY DESIGN

This is a five arm, single-blinded, randomized clinical trial. The study will be conducted according to the following steps for each individual:

Individuals aged 10-50 years will be invited to participate. They will be asked to provide informed consent and assent (for those under 18 years of age). After obtaining the informed consent and assent (if applicable), participants will undergo a screening including clinical evaluation and for the presence of microscopically detectable *P. falciparum* infection. Individuals with ≥ 16 gametocytes/ μL will be recruited and go through additional screening including haemoglobin measurement, CBC, assessment of renal and liver functions, and pregnancy tests. Recruitment will continue until 100 infected individuals with microscopically detectable *P. falciparum* gametocytes ($\geq 16/\mu\text{L}$) are recruited and randomised.

Individuals who meet the inclusion and exclusion criteria will be randomised in a 1:1:1:1:1 ratio into five groups (arms); ASAQ, ASAQ-PQ (0.25mg/kg), AL, ALAQ, ALAQ-PQ (**Table 1**). Randomisation will be performed by the study pharmacist. All other staff will be blinded to the treatment allocation.

Table 1. Treatment arms

Arm	ACT	PQ (mg/kg)	Sample size
1	ASAQ		20
2	ASAQ	0.25	20
3	AL		20
4	ALAQ		20
5	ALAQ	0.25	20

Each participant will be followed for 28 days. Participants will receive a full clinical and parasitological examination on days 2, 7, 14, 21, 28 after receiving the first dose of the study drugs. Blood samples will be taken at all visits for parasitology (microscopy, and whole blood for qRT-PCR) and serology with additional samples for haematology and biochemistry analysis at days 0, 2 and 14. A clinical and haematological examination will also be performed on day 1, at which point no other samples will be collected.

Infectivity to locally reared mosquitoes will be assessed with membrane feeding assays at baseline, on the final day of treatment (day 2) and at days 7 and 14 for all participants. Feeds will then be performed at day 21 for any individuals infectious at day 7 or 14; and at day 28 for any individuals infectious at day 14 or 21. Magnetic-activated cell sorting (MACS) to enrich for gametocytes will be done at two timepoints per individual, followed by MFA.

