7.2. Secondary outcome measures

- Median within person percent change (presented as percent reduction) in mosquito infection rate from baseline to all feeding time-points, with comparison within and between arms.
- Median mosquito infection rate at all feeding time-points, with comparison within treatment arms compared to baseline, and between arms.
- Infectivity to mosquitoes at all feeding time-points, with comparison within treatment arms compared to baseline, and between arms.
- Mean oocyst intensity (in all/all infected mosquitoes) at all feeding time-points, with comparison within treatment arms compared to baseline, and between arms.
- Male and female gametocyte prevalence at all time-points, determined by microscopy or molecular assays, with comparison within treatment arms compared to baseline, and between arms.
- Male and female gametocyte density at all time-points, determined by microscopy or molecular assays, with comparison within treatment arms compared to baseline, and between arms.
- Male and female gametocyte sex ratio (proportion male) at all time-points, determined by microscopy or molecular assays, with comparison within treatment arms compared to baseline, and between arms.
- Gametocyte circulation time (cumulative), determined by microscopy or molecular assays, compared between treatment arms.
- Gametocyte area under the curve (cumulative), determined by microscopy or molecular assays, compared between treatment arms.
- Asexual and total parasite prevalence at all time-points, determined by microscopy or molecular assays, with comparison within treatment arms compared to baseline, and between arms.
- Asexual and total parasite density at all time-points, determined by microscopy or molecular assays, with comparison within treatment arms compared to baseline, and between arms.
- Haemoglobin density at all time-points, with comparison within treatment arms compared to baseline, and between arms.
- Median within person percent change (presented as percent reduction) in haemoglobin density from baseline to all time-points, with comparison within and between arms.
- The frequency and prevalence of adverse events (all AE's, treatment related AE's, and haematological AE's) observed up to and including day 2, 7, and 14 post-treatment, and at all timepoints.

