8.2. Study procedures

Participants who agree to participate and provide written, informed consent will be assessed for the presence of sexual blood stage parasite with a thick blood film. Individuals with ≥ 16 gametocytes/ μL will go through additional screening for eligibility including haemoglobin measurement, CBC, assessment of the renal and liver functions and pregnancy tests. Recruitment will continue until 100 infected individuals with microscopically detectable *P. falciparum* gametocytes ($\geq 16/\mu\text{L}$) are recruited and randomised. Individuals with symptomatic malaria will not be enrolled in the study and will be treated with artemether + lumefantrine, the standard treatment for uncomplicated malaria as per the Ministry of Health policy in Mali. Individuals screened found with other acute diseases will also be treated according to the standard of care in Mali. Those with chronic disease will be referred to the district hospital for further evaluation and management.

Eligible patients will then be randomized (see below under randomization procedure) to one of the treatment groups, and drugs will be administered. In case of vomiting within 30 minutes after drug intake, the drugs will be re-administered once.

The participants will be compensated for any travel costs and for work loss income. Participants will be followed for 28 days as described in **Table 6** (below). Single venous draws or finger pricks will be used.

Any individuals determined to have an adverse event (haemolytic or otherwise) will be treated in accordance with national guidelines and best practice and will be withdrawn from the study at the discretion of the study clinician.

Table 6. Sampling framework for study participants

Required vacutainer	Time of sampling (d = day)	Required volume (mL)	Day 0	Day 1	Day 2	Day 7	Day 14	Day 21	Day 28
			V	C	V	V	V	V	V
Heparin (2-5mL)	Mosquito infectivity	2	*		*	*	*	**	**

	MACS	3	*		*				
EDTA (0.05-3.4mL)	Blood in RNA protect for RNA analysis/parasite genotyping	0.7	*		*	*	*	*	*
	Blood smear for asexual parasite and gametocyte density	0.1	*		*	*	*	*	*
	Filter paper blood spots	0.05	*		*	*	*	*	*
	Haemoglobin	0.05	*	*	*	*	*	*	*
	Plasma	1	*		*	*	*	*	*
	CBC	0.5	*		*	*	*		
	Human genotyping	1	*						
SST (0.8 mL)	Biochemistry	0.8	*		*	*	*		
	Maximum total Volume of blood sampled (mL)	38.65	9.2	0.05	9.2	6.2	6.2	3.9	3.9

\$ V denotes venous blood sampling and C denotes capillary sampling from a finger prick.

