9. SAFETY EVALUATION

The major safety endpoint is haemolysis. For this reason, haemoglobin will be measured before treatment, at days 1, 2, 7, 14, 21, and 28. Previous studies have shown that highest haemoglobin fall related to drug induced haemolysis can be detected within 7 days after treatment. In addition at 24 hours, and subsequent days of follow up, a questionnaire

assessing adverse events (AE) will be carried out. All participants will have access to contact study medical staff 24 hours a day and medical facilities that can give safe blood transfusions. Participants who require blood transfusions will be hospitalised at the district hospital in Ouelessebougou or referred to the University hospitals in Bamako for proper management. Additional safety precautions due to the small risk of transient haemolysis in this population will include the performance of clinical examinations and monitoring for adverse events (AE) at all sampling time points, carefree of charge to all participants throughout the duration of follow-up.

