11.1. Analysis plan

Mosquito infectivity will be assessed at three levels: the mean number of oocysts in a sample of mosquitoes (i.e. oocyst intensity), the proportion of mosquitoes infected with any number of oocysts (i.e. mosquito infection rate), and the infectivity of the study participant to any number of mosquitoes (i.e. infectivity to mosquitoes). The primary outcome measure will be the percent change in mosquito infection rate within each arm by day 2 compared to baseline, with other time-points of infectivity assessments as secondary outcomes. Percent change will be reported as percent reduction (with 100% as total reduction of transmission, and negative values as enhanced transmission). Other secondary transmission outcomes are as described in the 'Objectives' section above. Some exploratory objectives may be published separately from the main primary/secondary outcomes.

Statistical analysis will be conducted using the most recent STATA and SAS versions (16.0 and SAS version 9.4 at time of writing). Mosquito infection data will be analysed at time-points after baseline only for those individuals who are infectious at baseline, although the data and analyses from all enrolled individuals will be published in the appendix for completeness. Individuals will be classified as infectious to mosquitoes if they infect at least 1 mosquito, with any number of oocysts. Infectivity to mosquitoes and parasite/gametocyte prevalence will be compared within and between treatment arms using generalised linear models (family: binomial, z-score, co-efficient with 95% CI) or fishers exact tests. Absolute haemoglobin density and percent change in haemoglobin density (relative to baseline) will be compared using paired t-tests (t-score for difference compared to day 0) and two-way t-tests (t-score for difference between ACT matched treatment groups at each time-point). The proportion of gametocytes that are male will be calculated for all values with total gametocyte densities of 0.2/ μ L and over. Gametocyte circulation time will be calculated to determine the average period (in days) that a mature gametocyte circulates in the blood prior to clearance, using a deterministic compartmental model that assumes a constant rate of clearance and has a

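### Day-1 haemoglobin is a finger-prick value set against a venous day-0 value, so the within-arm day-1 change mixes sampling route with drug effect

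*Protocol*

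**What the plan says.** - **Sampling route.** In Protocol 8.2, the header of Table 6 codes day 0 as V, day 1 as C and days 2, 7, 14, 21 and 28 as V. The note explains: "V denotes venous blood sampling and C denotes capillary sampling from a finger prick". The day-1 column holds one item, haemoglobin, at 0.05 mL. The text of 8.2 is looser: "Single venous draws or finger pricks will be used".
- **Day-1 visit.** Section 5: "A clinical and haematological examination will also be performed on day 1, at which point no other samples will be collected".
- **Endpoint.** Section 9: "The major safety endpoint is haemolysis", and for that reason "haemoglobin will be measured before treatment, at days 1, 2, 7, 14, 21, and 28".
- **Outcomes.** Section 7.2 lists "Haemoglobin density at all time-points, with comparison within treatment arms compared to baseline, and between arms", and also the median within-person percent change "in haemoglobin density from baseline to all time-points, with comparison within and between arms". Table 5 includes day 1 among the haemoglobin visits.
- **Objective.** Section 4.2 is narrower. It compares haemoglobin with day 0 at the feeding visits only, and by Table 5 there is no feed on day 1.
- **Test.** Section 11.1: "Absolute haemoglobin density and percent change in haemoglobin density (relative to baseline) will be compared using paired t-tests", against day 0. It adds two-sample t-tests between ACT-matched arms at each time-point.
- **Device.** Section 10.6 names HemoCue without a specimen type. Section 10.7 also measures haemoglobin within the CBC at baseline and on days 2, 7 and 14. Nowhere is there a capillary reading at day 0, an adjustment for route, or an exclusion of day 1 from the paired tests.

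**The concern.** Every participant changes sampling route between day 0 and day 1. In a single arm, the mean day-1 change is the drug effect plus the mean capillary-venous difference, and no analysis of that arm alone can separate the two. If capillary blood reads lower, an apparent fall arises in every arm; if it reads higher, a true fall is hidden.

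Day 1 is the first haemoglobin reading after primaquine, which 6.2 gives on day 0. The synopsis states that G6PD status will not be tested, and 5.1 puts the frequency of deficiency at 10 to 15%. A within-arm p-value for early haemoglobin change is therefore likely to be read as evidence about haemolysis.

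**Working it through.** The protocol states no power or error rate for haemoglobin, so there is no figure of its own to reproduce.

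**Inputs from the protocol.** n = 20 per arm (Table 1); five arms; significance threshold 0.05 (11.1).

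**Assumed inputs.** Tests are two-sided, since 11.1 does not give sidedness for them. The SD of within-person change from day 0 to day 1 is 0.6-1.0 g/dL. The mean capillary-venous offset b is 0 to 0.5 g/dL in either direction.

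**Formula.** With no true change, the paired t statistic is noncentral t with 19 degrees of freedom and noncentrality λ = b / (SD/√20). The critical value is 2.093. For five independent arms, the chance of at least one significant result is 1 − (1 − p)^5.

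**False signal at day 1.**

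| Offset b (g/dL) | λ at SD 1.0 | p at SD 1.0 | λ at SD 0.6 | p at SD 0.6 |
|---|---|---|---|---|
| 0 | 0 | 5% | 0 | 5% |
| 0.2 | 0.894 | 13.6% | 1.491 | 29.4% |
| 0.3 | 1.342 | 24.7% | 2.236 | 56.5% |
| 0.5 | 2.236 | 56.5% | 3.727 | 94.2% |

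At least one of five arms:
- offset 0: 1 − 0.95^5 = 23%;
- offset 0.2 and SD 1.0: 1 − 0.864^5 = 52%;
- offset 0.2 and SD 0.6: 1 − 0.7065^5 = 82%.

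The reference for the five-arm figure is 23%, because five unadjusted tests already give that much with no offset.

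**Masking.** Take a true fall of 0.5 g/dL, SD 0.8 and a capillary value that reads b too high, so that the observed mean fall is 0.5 − b. Power is 75.5% at b = 0, 35.7% at b = 0.2, 18.6% at b = 0.3 and 5% at b = 0.5.

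**Between-arm test at day 1.** All arms use the same route, so b cancels from the difference in means. In 20,000 simulated two-sample tests with 20 per arm, SD 1 and a common offset of 0, 0.5 or 1.0 g/dL, rejection was 5.3%, 5.1% and 5.1%.

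**The 40% rule in 9.3.** An offset of 0.5 g/dL moves the percent change by 100 × 0.5/10 = 5.0 points at a baseline of 10 g/dL (the entry minimum) and by 100 × 0.5/14 = 3.6 points at an assumed baseline of 14 g/dL.

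**The case against.** **The offset is not in the documents.** Neither its existence, direction nor size is given, and with a zero offset the test is sound. This stands: the percentages show sensitivity and are not estimates. What the protocol does fix is a design in which an offset, if there is one, cannot be told apart from the drug effect.

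**A day-1 paired test may not be intended.** Section 4.2 limits comparison with day 0 to feeding visits, and 11.1 names no visits for the paired test. This stands in part. The day-1 test follows from the all-time-points wording of 7.2 together with Table 5, so the sections disagree and need to be aligned.

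**Table 6 may not describe the HemoCue sample at day 0.** The loose sentence in 8.2 does not forbid a finger prick at day 0. But Table 6 is the only visit-level statement of route, and it provides for none.

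**The contrast that matters is already planned and unbiased.** This is correct. ASAQ versus ASAQ-PQ and ALAQ versus ALAQ-PQ are the comparisons that can attribute a fall to primaquine. A route artefact would also show in the three arms without primaquine and could be recognised there.

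**A reader might infer that haemolysis monitoring as a whole is compromised.** The documents do not support that. Days 2 and 7 are venous against a venous baseline, and section 9 expects the largest drug-related fall to be detectable within 7 days. The 40% rule shifts by only a few points. The DSMB receives haemoglobin concentrations to day 14 (9.6), and no day-1 p-value triggers a stated decision.

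**Conclusion.** The point holds for one comparison only, the within-arm day-1 change from baseline, in absolute and percent terms. As 7.2 and 11.1 read, that test would be run on a capillary value against a venous one, with nothing to remove a difference in route.

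Under the stated assumptions, the per-arm chance of a spurious significant change rises from 5% to 14-29% at an offset of 0.2 g/dL and to 56-94% at 0.5 g/dL. At 0.2 g/dL, at least one of five arms is significant in 52-82% of trials, against 23% with no offset. If the true offset is zero there is no bias.

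It would be wrong to conclude that the primaquine contrasts, or any comparison from day 2 on, are biased by route. The consequence is moderate, but the test concerns the major safety endpoint and the repair is a matter of wording.

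**What to change.** 1. In 7.2 and 11.1, exclude day 1 from the within-arm paired haemoglobin tests, for both absolute value and percent change, and align both sections with 4.2. Editing 11.1 alone would leave the outcome list in 7.2 in conflict with it.
2. Report the day-1 change from baseline descriptively, labelled as capillary against venous.
3. Base day-1 inference on the ACT-matched between-arm contrasts already in 11.1.
4. State that haemoglobin change uses the HemoCue value at every visit and not the CBC haemoglobin. Otherwise a CBC baseline could add a device difference to the route difference. This step does not itself cure the route problem.

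The cost is the loss of a within-arm p-value at day 1, which could not be read as a drug effect in any case. No visit, sample or sample size changes.

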8.3. Randomization procedure

Eligible participants will be assigned the next sequentially numbered study ID number based on a pre-printed Study ID List created by a study investigator. Randomization will be computer generated using a 1:1:1:1:1 ratio. The randomisation codes will be provided in opaque sealed envelope to the study pharmacist. The study pharmacist in Mali will open the corresponding sealed, opaque envelope and provide the intervention to study participants. Randomization will be performed in blocks of varying sizes.

8.4. Blinding

This is a single-blind randomised controlled trial. The treating physician and staff involved with assessing all laboratory outcomes of the study are blinded, but no placebo will be used. The study pharmacist will be unblinded and responsible for randomisation and treatment administration. Entomology staff involved in the mosquito feeding assays will be blinded for the parasitology results.

9. SAFETY EVALUATION

The major safety endpoint is haemolysis. For this reason, haemoglobin will be measured before treatment, at days 1, 2, 7, 14, 21, and 28. Previous studies have shown that highest haemoglobin fall related to drug induced haemolysis can be detected within 7 days after treatment. In addition at 24 hours, and subsequent days of follow up, a questionnaire

assessing adverse events (AE) will be carried out. All participants will have access to contact study medical staff 24 hours a day and medical facilities that can give safe blood transfusions. Participants who require blood transfusions will be hospitalised at the district hospital in Ouelessebougou or referred to the University hospitals in Bamako for proper management. Additional safety precautions due to the small risk of transient haemolysis in this population will include the performance of clinical examinations and monitoring for adverse events (AE) at all sampling time points, carefree of charge to all participants throughout the duration of follow-up.

9.1. Definitions

9.1.1. Adverse events

Adverse events are defined as any undesirable experience occurring to a subject during the study, whether or not considered related to trial. An AE can therefore be any unfavourable and unintended sign (including an abnormal laboratory finding), symptom, or disease (new or exacerbated) temporally associated with a study intervention. AEs may include events that occur as a result of protocol-mandated procedures (i.e. invasive procedures). All AEs reported spontaneously by the subject or observed by the trial clinicians, or their staff will be recorded. Abnormal laboratory findings or other abnormal assessments that are judged by the trial clinicians to be clinically significant will be recorded as AEs or serious adverse events (SAEs) if they meet the definition. The investigators and trial clinicians will exercise their medical and scientific judgement in deciding whether an abnormal laboratory finding, or other abnormal assessment is clinically significant.

9.1.2. Serious adverse events

A serious adverse event is any untoward medical occurrence or effect that at any dose:

- Results in death
- Is life threatening (at the time of the event)
- Requires hospitalisation
- Results in persistent or significant disability or incapacity
- Congenital anomaly/birth defect
- Medically important event

All SAEs will be reported by the principal investigators to the Ethics Committees and DSMB within 48 hours of awareness of the PI.

9.1.3. Unexpected adverse events

An AE is considered unexpected if it is not listed in the Investigator's Brochure (IB) or Package Insert (for marketed products) or is not listed at the specificity or severity that has been observed.

9.1.4. Serious and Unexpected Suspected Adverse Reaction (SUSAR)

A SUSAR is any AE that is assessed as being serious, is suspected of having a causal relationship to the trial treatment and is unexpected (as per 3.2.4), will require expedited reporting to the Sponsor, RA and IRB/IEC which have approved the clinical trial and all other

organisations as required under the terms of the individual contracts (e.g. relevant pharmaceutical companies, NHS Trusts etc.).

Fatal or life-threatening SUSARs must be reported within 7 days of receipt of the report and all other SUSARs within 15 days (see Appendix 3 for reporting procedure for SUSARs for LSHTM sponsored trials).

9.1.5. Serious Unanticipated Problem (UP)

An UP is any event, incident, experience, or outcome that is

1. unexpected in terms of nature, severity, or frequency in relation to
 - a. the research risks that are described in the approved research protocol and informed consent document, IB, or other study documents; and
 - b. the characteristics of the subject population being studied; and
2. possibly, probably, or definitely related to participation in the research; and
3. places subjects or others at a greater risk of harm (including physical, psychological, economic, or social harm) than was previously known or recognized.

9.1.6. Unanticipated Problem that is not an Adverse Event (UPnonAE)

An UPnonAE is an UP that does not fit the definition of an adverse event, but which may, in the opinion of the investigator, involve risk to the subject, affect others in the research study, or significantly impact the integrity of research data. Such events would be considered a non-serious UP. For example, we will report occurrences of breaches of confidentiality, accidental destruction of study records, or unaccounted-for study drug.

All UPs that are also adverse events will be reported to the sponsor no later than 7 calendar days of site awareness of the event. UPs that are not AEs will also be reported to the sponsor.

